8.2 Severity

Hematologic adverse events will be graded using a modified iwCLL criteria (appendix 2).

All non-hematologic adverse events will be graded according to the NCI Common Terminology Criteria for Adverse Events (CTCAE) version 4.03. The CTCAE v4.03 is available at <http://ctep.cancer.gov/reporting/ctc.html>

If no CTCAE grading is available, the severity of an AE is graded as follows:

Mild (grade 1): the event causes discomfort without disruption of normal daily activities.

Moderate (grade 2): the event causes discomfort that affects normal daily activities.

Severe (grade 3): the event makes the patient unable to perform normal daily activities or significantly affects his/her clinical status.

Life-threatening (grade 4): the patient was at risk of death at the time of the event.

Fatal (grade 5): the event caused death.

8.3 Seriousness

A “serious” adverse event is defined in regulatory terminology as any untoward medical occurrence that:

1. Results in death.
If death results from (progression of) the disease, the disease should be reported as event (SAE) itself.
2. Is life-threatening.
(the patient was at risk of death at the time of the event; it does not refer to an event that hypothetically might have caused death if it were more severe).
3. Requires in-patient hospitalization or prolongation of existing hospitalization for ≥ 24 hours.
4. Results in persistent or significant disability or incapacity.
5. Is a congenital anomaly/birth defect
6. Is an important medical event
Any event that does not meet the above criteria, but that in the judgment of the investigator jeopardizes the patient, may be considered for reporting as a serious adverse event. The event may require medical or surgical intervention to prevent one of the outcomes listed in the definition of “Serious Adverse Event”.
For example: allergic bronchospasm requiring intensive treatment in an emergency room or at home; convulsions that may not result in hospitalization; development of drug abuse or drug dependency.

8.4 Relationship

Attribution categories for adverse events in relationship to protocol therapy are as follows:

- Definite – The AE *is clearly related* to the study treatment.
- Probable – The AE *is likely related* to the study treatment.
- Possible – The AE *may be related* to the study treatment.
- Unlikely – The AE *is doubtfully related* to the study treatment.
- Unrelated – The AE *is clearly NOT related* to the study treatment.

8.5 Prior experience

Expected events are those that have been previously identified as resulting from administration of the agent. An adverse event is considered unexpected, for expedited reporting purposes only, when either the type of event or the severity of the event is not listed in the current known adverse events listed in the agent clinical experience section of this protocol or the current product label.

8.6 Reporting Requirements for Adverse Events

8.6.1 Expedited Reporting

- The **Principal Investigator** must be notified within 24 hours of learning of any serious adverse events, regardless of attribution, occurring during the study or within 30 days of the last administration of the study drug.
- The **UCSD Human Research Protections Program (HRPP)** must be notified within 10 business days of “any unanticipated problems involving risk to subjects or

others” (UPR).

The following events meet the definition of UPR:

1. Any serious event (injuries, side effects, deaths or other problems), which in the opinion of the Principal Investigator was unanticipated, involved risk to subjects or others, and was possibly related to the research procedures.
 2. Any serious accidental or unintentional change to the IRB-approved protocol that alters the level of risk.
 3. Any deviation from the protocol taken without prior IRB review to eliminate apparent immediate hazard to a research subject.
 4. Any new information (e.g., publication, safety monitoring report, updated sponsor safety report), interim result or other finding that indicates an unexpected change to the risk/benefit ratio for the research.
 5. Any breach in confidentiality that may involve risk to the subject or others.
 6. Any complaint of a subject that indicates an unanticipated risk or that cannot be resolved by the Principal Investigator.
- The **FDA** will be notified within 7 calendar days of any unexpected fatal or life-threatening adverse event with possible relationship to study drug, and 15 calendar days of any event that is considered: 1) serious, 2) unexpected, and 3) at least possibly related to study participation.

8.6.2 Routine Reporting Requirements

- The UCSD HRPP will be notified of any adverse events that are not unanticipated problems involving risk to subjects or others (non-UPRs) at the time of the annual Continuing Review.
- The FDA will be notified of all non-serious adverse events annually at the time of the annual report.

9.0 AGENT INFORMATION

9.1 Dimethylfumarate

Please refer to package insert / prescribing information for more comprehensive information.

Other names for the drug: Tecfidera

Mechanism of action (or Product description): The mechanism of action of DMF is unknown. DMF and its metabolite, monomethyl fumarate (MMF) have been shown to activate the Nuclear factor (erythroid-derived 2)-like 2 (Nrf2) pathway *in vitro* and *in vivo* in animals and humans. The Nrf2 pathway is involved in the cellular response to oxidative stress. Preliminary studies in CLL have demonstrated inhibition of the Wnt pathway and other pro-survival pathways (eg: NFKB, JAK) in cancer cells, including CLL cells.

Availability: commercially available, will be provided for 8 weeks by the clinical trial.

How supplied: Available as hard gelatin delayed-release capsules in two strengths containing either 120 mg or 240 mg of dimethyl fumarate. The green and white 120 mg capsules are printed with “BG-12 120 mg” in black ink. The green 240 mg capsules are printed with “BG-12 240 mg”

in black ink.

Storage and stability: Store at 15 degrees C to 20 degrees C (59 to 86 degrees F). Protect the capsules from light. Store in original container. Once opened, discard bottles after 90 days.

Route of administration for this study: oral

Side effects:

Adverse reactions occurring in >10% of patients:

Cardiovascular: Flushing (40%)

Gastrointestinal: Abdominal pain (18%), diarrhea (14%), nausea (12%)

Infection: Infection (60%; placebo: 58%)

Adverse reactions occurring in 1% to 10%:

Dermatologic: Pruritus (8%), skin rash (8%), erythema (5%)

Gastrointestinal: Vomiting (9%), dyspepsia (5%)

Genitourinary: Proteinuria (6%)

Hematologic: Lymphocytopenia (2% to 6%)

Hepatic: Increased serum AST (4%)

Adverse reactions occurring in <1% (Limited to important or life-threatening): Eosinophilia (transient)

There are no contraindications listed within the manufacturer's U.S. product labeling.

Concerns related to adverse effects:

- Dermatitis/irritation: May cause rash, pruritus, or erythema. There are case reports of contact dermatitis resulting from dimethyl fumarate (DMF) exposure after use as a fungicide and desiccant in the shipping of furniture (Bruze, 2011; Giménez-Arnau, 2011; Ropper, 2012).
- Flushing: Commonly causes mild-to-moderate flushing (eg, warmth, redness, itching, burning sensation); flushing generally appears soon after initiation, and improves or resolves with subsequent dosing. Administration with food may decrease flushing incidence. The Canadian labeling suggests that a temporary dosage reduction or short-term (≤ 4 days) administration of aspirin (nonenteric coated) 30 minutes prior to dimethyl fumarate may also reduce the incidence and severity of flushing. Use of aspirin > 4 days has not been studied; long-term use of aspirin is not recommended.
- Gastrointestinal events: GI events (eg, nausea, vomiting, diarrhea, abdominal pain, dyspepsia) commonly occur with use; GI events generally occur in the first month of use and decrease thereafter. To improve tolerability, the Canadian labeling recommends administering with food or temporarily reducing the dosage.
- Hepatic effects: Transaminase elevations (usually <3 times ULN) were observed, generally occurring in the first 6 months of treatment.
- Lymphopenia: Decreased lymphocyte counts may occur with use. Prior to initiation, a recent CBC (within 6 months) should be reviewed to identify patients with preexisting low lymphocyte counts. Obtain CBC at least annually (or more frequently if indicated) during use. In trials, mean lymphocyte counts decreased ~30% over the first year of therapy (then stabilized), and lymphocyte counts increased (but did not return to baseline) 4 weeks following discontinuation. No difference in incidence of infection or series infections has

been observed in treated patients when compared to placebo; consider temporarily discontinuing therapy in patients with serious infections. Has not been studied in patients with preexisting low lymphocyte counts. Canadian labeling recommends treatment not be initiated in patients with signs/symptoms of a serious infection.

- Proteinuria: In clinical trials, proteinuria was reported at a slightly higher incidence than that observed with placebo; significance of these findings is unknown.

9.1.1 Return and Retention of Study Drug

Remaining drug is to be destroyed according to Moores Cancer Center Investigational Drug Services destruction policy.

9.1.2 Drug Accountability/Subject Compliance

Records of study medications used, dosages administered, and intervals between visits will be kept during the study. Patients will be asked to fill out a pill diary and bring with them for review after each cycle of study treatment. Drug accountability will be noted at the completion of the trial. Patients will be asked to return all unused medication at the end of the study.

10.0 STATISTICAL CONSIDERATIONS

10.1 Study Design/Study Endpoints

This is a single arm, open-label, non-randomized phase I study, to evaluate the tolerability, safety, and clinical activity of DMF. Relapsed/refractory CLL patients will be recruited. The primary endpoint is the maximum tolerated dose or biologically active dose and the rate of DLTs.

Secondary endpoints include the rate of adverse events including infections, the proportion of patients able to complete 2 months of therapy without intolerance or disease progression, the objective response rate (including partial response, complete response, or nodular complete response) by international working group in CLL guidelines (iwCLL), progression free survival, the change of expression of LEF1, c-myc, Wnt pathway, STAT pathway, and STAT1 phosphorylation.

10.1.1 Statistical Design

A standard 3+3 dose escalation design will be used. There are two test dose levels with a potential de-escalation dose. A minimum of three subjects will be treated at each dose level. All three subjects in a cohort will be evaluated for DLT in the defined DLT evaluation period (within 56 days of starting study treatment) before enrollment of subjects at the next dose level may begin. For all dose levels, if no DLTs are observed during the evaluation period among the three treated patients, escalation to the next dose level may begin. If a DLT is observed in one of the first three subjects in the cohort, the cohort will be expanded to six subjects. If zero or one of six subjects in the cohort experiences a DLT within the evaluation period, escalation to the next dose level will occur. If a DLT is seen in two or more subjects in a cohort, escalation will be stopped and the Maximum Tolerated Dose (MTD) will be considered to have been exceeded. The next lower dose will be considered as MTD if six patients have already been treated at that dose. Otherwise if only three patients have been treated at the next lower dose, then an additional three patients should be enrolled at the next lower dose level for a total of six

patients. If zero or one has DLTs among the 6 patients, then this dose is declared as MTD. Otherwise, there is further de-escalation according to the same scheme. As a result, the MTD is the highest dose where at most one-sixth of the patients developed DLT. If MTD is not reached, the higher dose will be selected. As with MTD, another 3 subjects will be treated at this dose if only 3 subjects have been treated.

1 additional cohort with 3 patients will be recruited at the selected dose to further evaluate the safety. The sample size of 9 subjects is considered to be sufficient to support preliminary tolerability, safety, and DLTs based on the established safety profile of this compound.

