5.0 TREATMENT PLAN

5.1 Treatment Dosage and Administration

For Dose Level 1, DMF (Tecfidera formulation) will be administered at a dose of 120 mg PO BID (approximately 12 hours apart) for 2 x 28 day cycles.

For Dose Level 2, DMF will be administered at the currently used dose for patients with multiple sclerosis: 120 mg PO BID for 1 week, then escalate to the dose of 240mg PO BID for the remainder of 2 x 28 day cycles. The 1 week lead-in at 120 mg is to assist in toleration and initial side effects and is as per the standard prescribing information.

For Dose Level 3, DMF will be administered at the currently used dose for patients with multiple sclerosis: 120 mg PO BID for 1 week, then escalate to the dose of 360mg PO BID for the remainder of 2 x 28 day cycles.

The medication can be taken with or without food. Capsules should not be crushed or chewed. Capsules will be self-administered on an outpatient basis. On days in which patients are scheduled for assessment, capsules will be taken in clinic. Missed or vomited doses will be skipped. Patients are assessed for safety and tolerability on Day 8, Day 1 of each subsequent cycle, and 28 days and 56 days following the last dose of DMF.

Dose Level	DMF dose (all cohorts start at 120 mg PO BID dose for 1 week, then increase to the assigned dose)
1	120 mg PO BID
2	240 mg PO BID
3	360 mg PO BID

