5.2 Definition of Dose-Limiting Toxicity

Dose Limiting Toxicity (DLT) is defined as any of the following adverse events that are considered by the investigator to be possibly, probably or definitely related to DMF within the DLT evaluation timeframe.

- Non-hematologic adverse events: grade 3 (CTCAE 4) or higher, lasting more than 7 days despite appropriate medical management.
- Hematologic adverse events: grade 3 (iwCLL 2008) or higher, lasting more than 7 days despite appropriate medical management, with the exception of: any grade lymphopenia ; or any grade lymphocytosis.
- Grade 4 non-hematologic (CTCAE 4) of any duration
- Grade 4 hematologic (iwCLL 2008) of any duration.
- Any clinically significant toxicity that precludes administration of the next scheduled dose beyond 14 days

Replacement patients may be enrolled for patients who withdraw from investigational treatment for a reason that is definitely unrelated to toxicity of the study agent or disease progression (e.g. patient preference, loss to follow-up). Replacement patients will ensure enough patients are enrolled to evaluate the primary endpoint.

The DLT evaluation timeframe is from the first dose of DMF until day 56 of the trial.

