5.7 Toxicities and Dosing Delays/Dose Modifications

Any patient who receives treatment on this protocol will be evaluable for toxicity. Each patient will be assessed for the development of toxicity according to the NCI Common Toxicity Criteria for Adverse Events (CTCAE), version 4.03 for non-hematologic adverse events, and 2008 international working group criteria (iwCLL, Hallek et al, appendix B) for hematologic adverse events. Dose adjustments should be made according to the system showing the greatest degree of toxicity. Patients are assessed for safety and tolerability on Day 8, Day 28, and Day 42 after starting DMF.

Toxicity – NCI CTCAE Grade (Hematologic- iwCLL)	Occurrence	Dose Modification
Non-hematologic		
Grade ≥ 3	1st	Withhold study treatment until resolved to Grade ≤ 1.

		Resume study treatment at the next lower dose level.
	Repeat	Discontinue therapy.
Hematologic*		
Grade \geq 3	1st	Withhold study treatment until resolved to ANC \geq 1000/mm ³ , hemoglobin is \geq 8 gm/dL, and platelet count \geq 50,000/mm ³ . Resume study treatment at same dose.
	2nd	Withhold study treatment until resolved to ANC \geq 1000/mm ³ , hemoglobin is \geq 8 gm/dL, and platelet count \geq 50,000/mm ³ . Resume study treatment at the next lower dose level.
	3rd	Permanently discontinue study treatment.
*Dose adjustments or dose holds for hematologic toxicity will apply even if the baseline values are lower than these thresholds due to heavily infiltrated marrow. In those cases, growth factors and/or blood product transfusion may be administered prior to continuing with DMF.		

Notes:

1. If any of the above are noted, the patient will be re-assessed within 7 days by the treating physician or investigator. Isolated laboratory abnormalities may be re-evaluated by laboratory draw only, or based on physician or investigator discretion.
2. DMF can be delayed for a maximum of 14 days; if not restarted in that time-span, study treatment will be permanently discontinued.
3. If dose is decreased for toxicity, dose re-escalation is not planned.
4. For invasive procedures, not including biopsies or venous catheter placement: withhold study treatment for 1 week prior to procedure, and at least 1 week following surgery until satisfactory wound healing has been achieved.

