6.3.2.8 Dispense DMF at assigned dose x 21 day supply

6.3.3 Visits 4: Day 1 of cycles 2

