6.3.3.8 Dispense DMF at assigned dose x 28 day supply

6.3.4 Visit 5: Between 1 day and 28 days after cycle 2 day 28: Primary Endpoint Response Assessment

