6.5 Removal of Subjects from Study Treatment and Study

Patients can be taken off the study treatment and/or study at any time at their own request, or they may be withdrawn at the discretion of the investigator for safety, behavioral or administrative reasons. The reason(s) for discontinuation will be documented and may include:

6.5.1 Patient completed study treatment;

6.5.2 Patient voluntarily withdraws from treatment (follow-up permitted);

6.5.3 Patient withdraws consent (termination of treatment and follow-up);

6.5.4 Patient is unable to comply with protocol requirements;

- 6.5.5 Patient demonstrates disease progression (unless continued treatment with study drug is deemed appropriate at the discretion of the investigator);
- 6.5.6 Patient experiences toxicity that makes continuation in the protocol unsafe;
- 6.5.7 Treating physician judges continuation on the study would not be in the patient's best interest;
- 6.5.8 Patient becomes pregnant (pregnancy to be reported along same timelines as a serious adverse event);
- 6.5.9 Development of second malignancy (except for basal cell carcinoma or squamous cell carcinoma of the skin) that requires treatment, which would interfere with this study;
- 6.5.10 Lost to follow-up.

If a research subject cannot be located to document survival after a period of 2 years the subject may be considered "lost to follow-up." All attempts to contact the subject during the two years must be documented.

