11.5 Adherence to the Protocol

Except for an emergency situation in which proper care for the protection, safety, and well-being of the study patient requires alternative treatment, the study shall be conducted exactly as described in the approved protocol.

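### Once a cohort has two DLTs, 10.1.1 redirects new enrolment but sets no dose for patients already assigned to the exceeded level; the default rules can restart a patient on that dose or step one up to it

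*Combined protocol and SAP*

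**What the plan says.** For a cohort with two or more DLTs, section 10.1.1 (and the synopsis, Statistical Methodology) states that "escalation will be stopped and the Maximum Tolerated Dose (MTD) will be considered to have been exceeded". What follows concerns enrolment only: if just three patients have been treated one level down, three more are added there. No dose is set for patients still on treatment at the exceeded level, and no moment is named at which the level counts as exceeded.

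Individual dosing follows the patient's own toxicity and calendar:

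- **5.7, first Grade 3 or higher hematologic event:** hold until ANC, hemoglobin and platelets meet fixed thresholds, then "Resume study treatment at same dose". A second event brings a step down; a third, or a hold beyond 14 days, ends treatment. A first Grade 3 or higher non-hematologic event already brings a step down.
- **5.2:** a hematologic event at least possibly related to DMF is a DLT if it is Grade 4 of any duration, or "grade 3 (iwCLL 2008) or higher, lasting more than 7 days despite appropriate medical management".
- **5.1:** "all cohorts start at 120 mg PO BID dose for 1 week, then increase to the assigned dose". On day 8, 6.3.2.8 reads "Dispense DMF at assigned dose x 21 day supply"; on day 1 of cycle 2, 6.3.3.8 reads "Dispense DMF at assigned dose x 28 day supply". Neither depends on the status of the level.
- **11.5:** outside emergencies, "the study shall be conducted exactly as described in the approved protocol".

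**The concern.** A 3+3 rule that finds a level too toxic should also protect the patients on it. Here it protects only those not yet enrolled. Two groups stand out. One is the patient who has just had a DLT at the level and, under the hematologic row of 5.7, goes back to it. The other is the patient who has not yet taken the dose and, under the day 8 dispensing step, is about to start it. For both, the written default gives a dose that the trial's own rule has judged too toxic, and avoiding it depends on someone choosing to intervene.

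**Working it through.** **The plan's own figure.** With the synopsis's three levels and a three-patient expansion, the stated 15 to 21 reproduces: 3 + 3 + 6 + 3 = 15 and 3 × 6 + 3 = 21. Nothing below changes it.

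**Assumptions.** The level is treated as exceeded on the day the second DLT is seen, and held days are not made up. The text settles neither.

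**Case (a), same-dose restart.** Inputs: 5.2, 5.7, Appendix B and the 56-day course. At Levels 2 and 3, the first scheduled blood count after step-up is cycle 2 day 1, nominally day 29. Days left from day d are 56 − d + 1.

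- Grade 3 first seen on day 29 has lasted more than 7 days, and so becomes a DLT, on day 37. Restart then leaves 56 − 37 + 1 = 20 days at the level. With the longest permitted hold (14 days), restart is on day 43 and leaves 56 − 43 + 1 = 14.
- Grade 4 first seen on day 29 is a DLT at once. The 14-day hold again leaves 14 days; a 7-day hold (restart day 36) leaves 21.
- The hold can be shorter still, because Appendix B grades platelets by percentage fall while 5.7 restarts on an absolute count. A fall from 240,000 to 55,000 is (240 − 55)/240 = 77.1%, which is Grade 4, yet 55,000 already meets the 50,000 restart threshold for platelets.

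**Case (b), step-up from the lead-in.** Level 1 is already 120 mg, so this concerns Levels 2 and 3. Day 8 to day 56 is 56 − 8 + 1 = 49 days at the exceeded dose. Any two DLTs can trigger it, including non-hematologic ones. If the second DLT falls on that patient's day d, a patient who entered g days later is on day d − g, and is in the lead-in when g lies between d − 7 and d − 1:

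| Second DLT | Gap to the lead-in patient |
|---|---|
| Day 16 to 28 (a Grade 3 event starting on day 8 becomes a DLT on day 16) | 9 to 27 days |
| Day 29 (Grade 4 hematologic) | 22 to 28 days |
| Day 37 (Grade 3 hematologic first seen on day 29) | 30 to 36 days |

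The first row is plausible because 9.1 places most GI reactions in the first month. The documents give no accrual rate. Spreading 15 to 21 patients over the two-year study duration gives one every 730/21 = 35 to 730/15 = 49 days. If the last patient's treatment and one-year follow-up must also fit, it is (730 − 56 − 365)/21 = 15 to 309/15 = 21 days. These averages ignore the 56-day waits between levels, so they are not within-cohort gaps. They show that case (b) is possible, not that it is likely.

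**How many patients.** A cohort of three has at most three patients at the level. Under 10.1.1 a single DLT expands the cohort to six, so more than three can be affected.

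**Do the existing controls close the gap?**

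- 5.7 requires re-assessment within 7 days, but then applies the same-dose restart.
- 5.8, 6.5.6 ("Patient experiences toxicity that makes continuation in the protocol unsafe") and 6.5.7 permit stopping, on judgment about the individual patient.
- 8.6.1 takes serious events to the principal investigator within 24 hours, without a dosing consequence.
- 11.5.1 permits emergency changes.
- 11.4 provides DSMB reports every six patients, or earlier where a stopping rule calls for it, but sets no dose.

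Each allows intervention. None requires a lower dose once the level is exceeded.

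**The case against.** The strongest counter-argument is timing. The DLT window and the treatment course are the same 56 days. If a level is judged only at an end-of-window cohort review, the first three patients have finished study drug and there is nobody to protect. That reading is open, and so the conclusion is conditional. But the text does not require waiting, and a trial that acted on the second DLT at once would meet the gap.

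Second, discretion is substantial. Stopping a patient for unacceptable toxicity is itself within the protocol. A reader might infer that 11.5 compels a restart after a DLT; it does not, because 5.8 and 6.5 are part of what must be followed. The same-dose restart is the default, not an obligation. The DSMB clause could also be read as triggered by two DLTs, though it does not say so.

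Third, case (a) is narrow. Non-hematologic events already step down, lymphopenia is excepted from the Grade 3 or higher hematologic DLT criterion, and the only other hematologic reaction in 9.1 is rare transient eosinophilia. This stands.

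Fourth, 5.1 uses escalation language for the day 8 step-up, so stopping escalation might be stretched to cover it. In 10.1.1, however, the term means moving between dose levels.

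Fifth, Level 2 is the approved dose in multiple sclerosis and Level 3 was tested in psoriasis. That lowers prior concern, but it does not answer two DLTs observed in CLL patients.

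**Conclusion.** The gap is real and worth closing. It is a participant-safety improvement, conditional on the level being declared exceeded when the second DLT is seen. Case (b) has the wider trigger and the longer exposure, but needs staggered entry. Case (a) needs a first hematologic DLT that recovers within 14 days, and should be uncommon.

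Two stronger readings are not supported. A reader might infer that the MTD or the DLT-rate estimate is biased. It is not: the DLT count that triggers the rule is unchanged, and 10.4 estimates the rate at the selected dose. A reader might also want to total the patient-days spent at an exceeded level. The documents give neither the accrual pattern nor the hematologic share of DLTs. Such a total would also include DLT-free patients already tolerating the dose, for whom continuing can be a defensible choice.

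**What to change.** Add to 10.1.1 and the synopsis, with cross-references in the hematologic row of 5.7 and in 6.3.2.8:

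> A level is declared above the MTD as soon as a second DLT is confirmed in the cohort. From then, a patient who had a DLT at that level does not resume or continue at it: treatment goes on at the next lower level, or stops at Level 1. This overrides the same-dose restart in 5.7. A patient still in the 120 mg lead-in steps up no further than the next lower level. Other patients without a DLT may continue or step down, with the investigator's documented benefit-risk decision. All such patients stay in their assigned level for the DLT count and the 10.4 summaries, with actual dose reported. They are not counted among the six, or among patients who received the selected dose, at the lower level.

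The last two sentences keep stepped-down patients out of the lower level's MTD decision and out of the 10.4 completion proportion at the selected dose.

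The cost is one short paragraph and two cross-references by amendment, with no extra patients and no change to the decision rule. The downside is that a few patients get lower exposure or, at Level 1, lose DMF on study, sometimes at a dose that is in fact tolerable. With assumed true DLT rate p and q = 1 − p, a level is declared exceeded with probability 1 − [q³ + 3pq² × q³]. This is 0.09 at p = 0.1 and 0.29 at p = 0.2. It counts DLTs of any cause and includes expansion to six, so it measures how often the rule would be invoked at a fairly tolerable dose, not how often case (a) or (b) would arise.
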